6.4. Packaging and Labeling

The test articles will be packaged in blisters as the primary packaging. The test article will be over-labeled to mask the subject to the identity of the lens. The test articles will be in investigational cartons sealed with a tamper evident seal, commercial cartons, or in plastic bags as the secondary packaging form. The sample study label is shown below:

Control Lens Label	Test Lens Label

 
Exclusively for Clinical Investigations For Use in Clinical Study CR-CR# Only
 <hr/> 
Contents: Six contact lenses in solution. Sponsored by: Johnson & Johnson Vision Care, Inc. [name], USA
 
 
 STERILE  
   
 
	
 
Exclusively for Clinical Investigations For Use in Clinical Study CR-CR# Only
 <hr/> 
Contents: One contact lens in solution. Sponsored by: Johnson & Johnson Vision Care, Inc. [name], USA
 
 
 STERILE  
   
 

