5. TEST ARTICLE ALLOCATION AND MASKING

5.1. Test Article Allocation

Participants will wear all study lenses in a bilateral fashion. There will be three levels of randomization in this study: (1) Sequence of driving time (Day and Night) (2) Sequence of lens wear (Test, Control1 and Control2) and (3) Driving Route (A, B, C). Hazard and pedestrian locations will be randomized for each driving route.

Subjects will be first randomly assigned to one of two possible driving time sequences (Day/Night and Night/Day) using a 2x2 crossover design. Within each driving time (Day and Night) subjects will be randomly assigned to one of six possible lens wear sequences using a 3x3 Williams crossover design:

Table 1: 3x3 Williams design

Sequence	Period1	Period 2	Period 3
1	Test	Control 1	Control 2
2	Test	Control 2	Control 1
3	Control 1	Test	Control 2
4	Control 1	Control 2	Test
5	Control 2	Test	Control 1
6	Control 2	Control 1	Test

This design is balanced with respect to first carry-over effect as every treatment follows every other treatment the same number of times.

Within each time and lens type combination subjects will be randomized to a driving route (Route1, Route2 and Route3) to further reduce the potential for treatment bias. The randomization scheme will be generated using the PROC PLAN procedure from SAS Software Version 9.4 or higher (SAS Institute, Cary, NC). The study site must follow the randomization scheme provided and complete enrollment according to the randomization list and not pre-select or assign subjects.

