5.2. Masking

Every effort will be made to mask both the subject and the investigator, in order reduce potential bias where possible. Subjects will be masked to the identity of the investigational product when only a contact lens correction is worn. However, if subjects perceive a change in light levels during Test contact lens wear, they may become aware of the product being tested.

Subjects will also be aware of the test condition when the ACUVUE® OASYS® Brand Contact Lenses with HYDRACLEAR® PLUS is worn with Transitions® XTRActive™ – Gray Spectacles (Control 2) as the other test conditions will involve contact lens wear with a spectacle frame without spectacle lenses.

Investigators involved in the on-road driving data collection (clinical personnel within the vehicle) will be partially-masked as to the identity of the investigational product (i.e. another investigator will fit the contact lenses prior to the driving assessment).

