3.6.	Randomization	
Refer to pre-determined randomization order of testing (counter balancing) for the three test treatments. The final contact lens powers found in Visit 1 will be used.
 
 • Test contact lenses (worn with spectacle frame without lenses) • OASYS clear contact lenses (worn with spectacle frame without lenses) • OASYS clear contact lenses (worn with photochromic spectacles) 	
3.7.	Lens Insertion	
The Investigator or the subject inserts the study lenses. Record the time of lens insertion. Check for lens damage under the slit lamp before proceeding with lens settling. Replace damaged lenses if applicable.
	
3.8.	Lens Settling	
Allow the study lenses to settle for a minimum of 15 minutes.
 
Note: for nighttime testing, sufficient time is allowed for the subject to dark adapt.
	
3.9.	Pupillometry	
Measure the right eye pupil diameter during distance fixation (3 measures) using NeurOptics Pupillometer while subject seated in vehicle.
 
EDC: record pupil diameters in mm (0.1 mm increments)
	
3.10.	Illuminance levels	
Measurement of lighting level on the track outside the vehicle and at the plane of the eye in the vehicle.
 
 • For daytime testing, the illuminance must be > 1000 lux. • For nighttime testing, the illuminance must be < 10 lux. 
EDC: record outside and inside illuminance in lux rounded to the nearest whole number.
	

Visit 3: Closed-circuit on-road driving performance 1 (Day/night condition based on randomization)			
Step	Procedure	Details	
3.11.	Driving assessment	
Subject performs three laps of the circuit while under assessment. Measurements recorded include:
 
 1. Sign recognition 
 a. EDC: record % signs correctly identified b. EDC: record distance to signs in meters 2. Hazard avoidance 
 a. EDC: record % hazards hit 3. Driving time 
 a. EDC: record lap time in seconds b. EDC: record the % time in wrong lane 4. Pedestrian recognition distance 
 a. EDC: record distance to recognition in meters 
A composite driving Z score will be calculated afterwards using measures listed above.
	
3.12.	Subjective Questionnaire	Administer subjective questionnaire regarding driving task just completed. This will be a paper-administered questionnaire.	Appendix A

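### The sample over-labels in Protocol 6.4, meant to mask the subject, differ between Control and Test (six lenses against one), and nothing keeps labelled or branded packs out of the subject's sight

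*Protocol*

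**What the plan says.** Protocol 6.4 (Packaging and Labeling) states the purpose of the over-label: "The test article will be over-labeled to mask the subject to the identity of the lens". On packaging levels it says "The test articles will be packaged in blisters as the primary packaging", and it lists the permitted outer packs as "investigational cartons sealed with a tamper evident seal, commercial cartons, or in plastic bags as the secondary packaging form". It then shows two sample labels. The readable text is the same on both except for the contents line, which is "Contents: Six contact lenses in solution" under the Control heading and "Contents: One contact lens in solution" under the Test heading.

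Protocol 5.2 (Masking) promises that "Subjects will be masked to the identity of the investigational product when only a contact lens correction is worn". It concedes two ways in which a subject may recognise a condition: a perceived change in light level with the Test lens, and the spectacles worn in Control 2. Packaging is not among them. The same section has one investigator fit the lenses and other staff collect data in the vehicle, so that the latter are partially masked.

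At each lens insertion step in Protocol 7.2, including the driving visits, "The Investigator or the subject inserts the study lenses". Table 2 in Protocol 6.1 gives the commercial OASYS lens for both Control 1 and Control 2.

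**The concern.** A label used for masking should not vary by arm, and these do. The promise in 5.2 covers the two conditions worn with an empty frame, Test and Control 1, which form the primary comparison. The Protocol synopsis calls the study partially masked with respect to the subject, and SAP 1.3 calls it single-masked. Subject masking is therefore the main masking that the plan claims.

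It matters for this endpoint because the composite depends partly on what the driver chooses to do: when to press the recognition button for the pedestrian, whether to call a sign or hazard, how fast to drive and where to keep in the lane. A driver who knows or suspects which lens is in the eye may behave differently. The documents do not indicate the direction or size of any such change.

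**Working it through.** There is no plan figure to reproduce and no calculation to make. The check sets the relevant sections side by side.

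1. **Do the labels differ by arm?** Yes. Protocol 6.4 shows six lenses for Control and one for Test, and the rest of the readable text is identical.

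2. **Which pack carries the label?** Protocol 6.4 does not say. Table 2 lists a blister for all three conditions.
   - If the label goes on single blisters, the Control text is wrong, since a blister does not hold six lenses.
   - If the Control label belongs on a carton and the Test label on a single-lens pack, the arms are packaged visibly differently and no Control blister label is shown.
   - Either way, 6.4 needs a correction or a clarification.

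3. **Can the subject see the packs?** Subjects may insert the lenses themselves (7.2). Section 6.7 keeps stock in a locked cabinet open only to assigned dispensing staff, which limits access to stored stock. It does not govern what is in view when a lens is opened at a visit, and no other section does.

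4. **Can the subject turn a count into a product?** Not from one label alone, because no product or arm name is printed on it. A key is needed, and the design can supply one. Control 2 is recognisable from its spectacles (5.2) and uses the same OASYS lens as Control 1 (6.1). Suppose a subject knows that the two controls share a lens and has seen the Control 2 pack. A frame-only pack with the same count then points to Control 1, and one with a different count points to Test. This takes at least two sightings plus that knowledge.

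5. **When is the key available?** In Table 1 of Protocol 5.1, sequences 1 to 4 (4 of 6) begin with a frame-only condition, so within those sessions the first period comes before any Control 2 reference. However, all three conditions are tested at Visit 2, before either driving visit, so a key learned there could be carried forward.

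6. **Commercial cartons.** Protocol 6.4 neither ties them to an arm nor says that their branding is covered. Table 2 describes both controls as commercial product, so the control lens is their most natural content. An uncovered brand name would make the key in step 4 unnecessary.

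**The case against.** The case against is substantial, and most of it limits the point rather than removing it.

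- **Templates.** The labels are samples with an unfilled study-number placeholder, and the arm names are headings in the protocol table, not label text. This stands. A reader might infer that anyone who sees the packaging can name the lens, and the documents do not support that.
- **Pack level and exposure.** A six-lens label presumably belongs on an outer pack. The study is non-dispensing, and no step has a subject handle a carton. This also stands: exposure is possible but not shown. Test and Control 1 are worn at Visits 2, 3 and 4, and under SAP 1.3 Test and one control are worn at Visit 1, so a reader might count 3 × 2 + 2 = 8 exposures. Those are wearings. If the investigator inserts the lenses, sightings could be none.
- **One sighting.** A reader might infer that a single label reveals all three assignments in a session. It does not. A key is needed, and under Table 1 each first-period condition is followed by either of the other two, so a Period 1 sighting never reveals Period 2.
- **Cartons.** Table 2 is titled as a list of test articles and includes both controls, so the over-label may be meant for them too. That is a fair reading, but 6.4 does not say that it covers commercial branding.
- **Size.** It is tempting to express an expectation effect as a share of the 0.25 margin. The documents give no figure from which to do so.
- **Randomisation list.** Protocol 5.1 says "The study site must follow the randomization scheme provided and complete enrollment according to the randomization list". A reader might infer that the whole site holds the list, but the text does not say who holds it.
- **Disclosed limits.** The plan calls its masking partial and admits that the Test lens may be noticed through light levels. Neither statement covers a label that differs by arm.

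**Conclusion.** The labelling shown in Protocol 6.4 conflicts with its stated purpose and with the subject masking of Test against Control 1 promised in 5.2. A subject who sees the labelled packs and can link count to product could tell the two apart, and the protocol contains nothing to prevent it.

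The conclusion rests on two conditions that the documents neither confirm nor exclude: that packs are in the subject's view, and that the subject has a key such as the Control 2 pack or an uncovered brand name. The effect on the driving score, in size or direction, cannot be computed. The point does not show that masking will fail or that the primary result would be biased. It identifies an avoidable gap in protecting the primary contrast, and it should be closed because doing so is cheap.

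**What to change.** In Protocol 6.4:

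1. Specify one identical, coded over-label with a single-lens contents line for the individual blisters of both lens types, and state that this is the level at which the masking label is applied.
2. Have the fitting investigator already planned in 5.2 remove blisters from any carton or bag out of the view of the subject and in-vehicle staff, so that packs bearing a count or a brand are never seen by them. Add a cross-reference in 5.2.

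The cost is a small relabelling effort and a short handling rule at the site. No subjects, visits, staff or analyses are added.

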6.5. Storage Conditions

Test articles will be maintained at ambient temperatures at the clinical site. Test articles must be kept under secure conditions.

6.6. Collection and Storage of Samples

No samples will be collected as part of the study procedures. When possible, any lens or test article associated with an Adverse Events and/or a Product Quality Complaint must be retained and stored in a glass vial with moderate solution pending directions from the sponsor for potential return to JJVC.

6.7. Accountability of Test Articles

JJVC will provide the Investigator with sufficient quantities of study articles and supplies to complete the investigation. The Investigator is asked to retain all lens shipment documentation for the test article accountability records.

Test article must be kept in a locked storage cabinet, accessible only to those assigned by the Investigator for dispensing. The Investigator may delegate this activity to authorized study site personnel listed on the Site Delegation Log. All test articles must be accounted. This includes:

1. What was dispensed for the subject for trial fitting, to wear out of the office, or issued for the subject to replace appropriately between visits
2. What was returned to the Investigator unused
3. The number and reason for unplanned replacements.

The Investigator will collect all unused test articles from the subjects at the end of the subject's participation. Subject returned unused test articles must be separated from the clinical study inventory of un-dispensed test articles, and must be labeled with the subject number and date

of return. Following final reconciliation of test articles by the monitor, the Investigator or monitor will package and return all unused test articles to JJVC.

If there is a discrepancy between the shipment documents and the contents, contact the study monitor immediately.

[REDACTED]: Site Instructions for Test Article Receipt and Test Article Accountability for additional information.

7. STUDY EVALUATIONS

7.1. Time and Event Schedule

Table 3: Time and Events

Visit Information	Visit 1 Screening, Contact lens fit	Visit 2 Laboratory measurements	Visit 3 Closed track day/night time driving	Visit 4 Closed track day/night time driving
Time Point	Day 1	> 24 hours after Visit 1	> 24 hours after Visit 2	> 1 week after Visit 3
Estimated Visit Duration	1 hour	1.5 hours	2.5 hours	2.5 hours
Statement of Informed Consent	X			
Demographics	X			
Medical History/Concomitant Medications	X			
Inclusion/Exclusion Criteria	X			
Habitual Contact Lens Information	X			
Compliance and Subject Reported Ocular Symptoms and Adverse Event Review	X			
Entrance Snellen Distance Visual Acuity	X	X		
Subjective Sphero-Cylindrical Refraction	X			
Subjective Best Sphere Refraction	X			
Slit Lamp Classification Scale	X	X		
Lens Insertion & Settling	X	X	X	X
Lens Fit Assessment	X	X		
Order required lenses	X			
Visual acuity measurements	X	X		

Visit Information	Visit 1 Screening, Contact lens fit	Visit 2 Laboratory measurements	Visit 3 Closed track day/night time driving	Visit 4 Closed track day/night time driving
Time Point	Day 1	> 24 hours after Visit 1	> 24 hours after Visit 2	> 1 week after Visit 3
Estimated Visit Duration	1 hour	1.5 hours	2.5 hours	2.5 hours
Contrast sensitivity measurements		X		
Pupillometry		X	X	X
Post lens wear slit lamp evaluation	X	X		
Measurement of illuminance levels			X	X
On road driving assessment			X	X
Subjective driving questionnaires			X	X
Study completion				X

7.2. Detailed Study Procedures

VISIT 1

Visit 1: Screening			
Step	Procedure	Details	
1.1	Statement of Informed Consent	Each subject must read, understand, and sign the Statement of Informed Consent before being enrolled into the study. The Principal Investigator or his/her designee conducting the informed consent discussion must also sign the consent form. Note: The subject must be provided a signed copy of this document.	
1.2	Demographics	Record the subject's date of birth, gender, race and ethnicity.	
1.3	Medical History and Concomitant Medications	Questions regarding the subjects' medical history and concomitant medications.	
1.4	Habitual Lenses	Questions regarding the subject's habitual lens type and parameters.	
1.5	Iris Color	The investigator will record the subject's iris color based on the scale provided.	Appendix E

Visit 1: Screening			
Step	Procedure	Details	
1.6	Eligibility after Screening	All responses to Screening Inclusion Criteria questions must be answered “yes” and all responses to Exclusion Criteria must be answered “no” for the subject to be considered eligible.	

Visit 1: Baseline			
Step	Procedure	Details	
1.7	Entrance Visual Acuity	Record the distance logMAR visual acuity (OD, OS, and OU) to the nearest letter with their habitual correction in place. Subjects must read the smallest line until at least 50% of the letters are read incorrectly. EDC: record logMAR acuity	
1.8	Subjective Spherocylindrical Refraction	Complete subjective spherocylindrical refraction and record the resultant distance logMAR visual acuity (OD, OS and OU) to the nearest letter.	
1.9	Subjective Best Sphere Refraction	Perform subjective best sphere refraction with a phoropter (adopt the maximum plus to maximum visual acuity (MPMVA) approach and use the duo-chrome test for binocular balancing) and record the best corrected distance logMAR visual acuity (OD, OS, OU) to the nearest letter. Note: The endpoint criterion for the duo-chrome test is the lens power at which the red and green sides of the chart appear to be equally distinct. However, if the subject’s response changes from “red” to “green” with only a 0.25D change in power and no report that the two sides appear to be equally sharp, the refraction endpoint should be the lens power that leave the red chart sharper.	

Visit 1: Baseline			
Step	Procedure	Details	
1.10	Slit Lamp Findings	
FDA Slit Lamp Classification Scale will be used to grade the findings and determine eligibility.
 
If any of these slit lamp findings are grade 3 or higher, the subject may not continue at this time, but may return up to one additional time to determine eligibility. If discontinued a final examination must be completed.
 
If the clearance of the fluorescein needs to be expedited, preservative-free rewetting drops or saline may be instilled.
	
1.11	Eligibility after Baseline	All responses to Inclusion Criteria questions must be answered “yes” and all responses to Exclusion Criteria questions must be answered “no” for the subject to be considered eligible.	

Visit 1: Trial Lens Fitting 1			
Step	Procedure	Details	
1.12	Lens Selection	
Select the trial contact lens based on the randomization scheme.
 
Select the trial contact lens power based on subjective best sphere refraction.
	
1.13	Lens Insertion	The Investigator or the subject inserts the study lenses. Record the time of lens insertion. Check for lens damage under the slit lamp before proceeding with lens settling. Replace damaged lenses if applicable.	
1.14	Lens Settling	Allow the study lenses to settle for a minimum of 15 minutes. A Patient Instruction Guide will be provided to the subject.	

Visit 1: Trial Lens Fitting 1			
Step	Procedure	Details	
1.15	Subjective Best Sphere Over Refraction	
Perform subjective best sphere refraction over the study lenses with a phoropter (adopt the maximum plus to maximum visual acuity (MPMVA) approach and use the duo-chrome test for binocular balancing) and record the best corrected distance logMAR visual acuity to the nearest letter (OD, OS, OU).
 
Note: The endpoint criterion for the duo-chrome test is the lens power at which the red and green sides of the chart appear to be equally distinct. However, if the subject's response changes from "red" to "green" with only a 0.25D change in power and no report that the two sides appear to be equally sharp, the refraction endpoint should be the lens power that leave the red chart sharper.
	 
1.16	Lens Power Modification (if applicable)	
Adjust the lens power if the subject's best sphere over-refraction is not plano.
 
For each power modification, repeat steps (1.13 - 1.16).
 
One power modification is allowed.
	
1.17	Visual Acuity	
Record the distance logMAR visual acuity (OD, OS, and OU) to the nearest letter with the study contact lenses in place. Subjects must read the smallest line until at least 50% of the letters are read incorrectly.
 
EDC: record logMAR acuity
	
1.18	Subjective Lens Fit Assessment	
Subjective Assessment of the Lens Fit. If the fit is graded as unacceptable based on the criteria below, then the subject is discontinued from the study and will be replaced.
 
 1. Limbal exposure in any gaze 2. Edge lift 3. Insufficient and/or excessive movement in all three movement categories 	

Visit 1: Trial Lens Fitting 1			
Step	Procedure	Details	
1.19	Continuance	
For the subject to continue in the study, they must meet all three of the following criteria:
 
 1. Visual acuity is 0.1 logMAR (20/25) or better OD and OS 2. The lens fit is acceptable OD and OS 3. Investigator approval. If the Investigator does not approve the dispensing of the first study lens, then the study is terminated for that subject. 	
1.20	Lens removal	The study lens will be removed and discarded.	

Visit 1: Trial Lens Fitting 2			
Step	Procedure	Details	
1.21	Lens Selection	
Select the alternate trial contact lens based on the randomization scheme.
 
Select the trial contact lens power based on subjective best sphere refraction.
	
1.22	Lens Insertion	
The Investigator or the subject inserts the study lenses. Record the time of lens insertion.
 
Check for lens damage under the slit lamp before proceeding with lens settling.
 
Replace damaged lenses if applicable.
	
1.23	Lens Settling	Allow the study lenses to settle for a minimum of 15 minutes.	

Visit 1: Trial Lens Fitting 2			
Step	Procedure	Details	
1.24	Subjective Best Sphere Over Refraction	
Perform subjective best sphere refraction over the study lenses with a phoropter (adopt the maximum plus to maximum visual acuity (MPMVA) approach and use the duo-chrome test for binocular balancing) and record the best corrected distance logMAR visual acuity to the nearest letter (OD, OS, OU).
 
Note: The endpoint criterion for the duo-chrome test is the lens power at which the red and green sides of the chart appear to be equally distinct. However, if the subject's response changes from "red" to "green" with only a 0.25D change in power and no report that the two sides appear to be equally sharp, the refraction endpoint should be the lens power that leave the red chart sharper.
	 
1.25	Lens Power Modification (if applicable)	
Adjust the lens power if the subject's best sphere over-refraction is not plano.
 
For each power modification, repeat steps (1.21 - 1.24).
 
One power modification is allowed.
	
1.26	Visual Acuity	
Record the distance logMAR visual acuity (OD, OS, and OU) to the nearest letter with the study contact lenses in place. Subjects must read the smallest line until at least 50% of the letters are read incorrectly.
 
EDC: record logMAR acuity
	
1.27	Subjective Lens Fit Assessment	
Subjective Assessment of the Lens Fit. If the fit is graded as unacceptable based on the criteria below, then the subject is discontinued from the study and will be replaced.
 
 1. Limbal exposure in any gaze 2. Edge lift 3. Insufficient and/or excessive movement in all three movement categories 	

Visit 1: Trial Lens Fitting 2			
Step	Procedure	Details	
1.28	Continuance	
For the subject to continue in the study, they must meet all three of the following criteria:
 
 1. Visual acuity is 0.1 logMAR (20/25) or better OD and OS 2. The lens fit is acceptable OD and OS 3. Investigator approval. If the Investigator does not approve the dispensing of the first study lens, then the study is terminated for that subject. 	
1.29	Lens Removal	The study lens will be removed and discarded.	
1.30	Exit Slit Lamp Biomicroscopy	
FDA Slit Lamp Classification Scale will be used to grade the findings.
 
If any of these slit lamp findings are grade 3 or higher, the subject is classified as having an adverse event. Adverse events shall be documented and followed until resolved, at which time they will be terminated from the study.
 
If the clearance of the fluorescein needs to be expedited, preservative-free rewetting drops or saline may be instilled.
	
1.31	Exit Visual Acuity	
Record the distance logMAR visual acuity (OD, OS, and OU) to the nearest letter with their habitual correction in place. Subjects must read the smallest line until at least 50% of the letters are read incorrectly.
 
EDC: record logMAR acuity
	

VISIT 2

Visit 2: Laboratory measures of vision performance			
Step	Procedure	Details	
2.1.	Adverse Events and Concomitant Medications Review	
Review the subject's concomitant medications and record any changes from the previous study visit.
 
Record any adverse events or medical history changes from the previous study visit.
	
2.2.	Entrance Visual Acuity	
Record subjects' distance logMAR visual acuity, OD, OS and OU to the nearest letter with habitual correction in place. Subjects must read the smallest line until at least 50% of the letters are read incorrectly.
 
EDC: record logMAR acuity
	
2.3.	Slit Lamp Findings	
FDA Slit Lamp Classification Scale will be used to grade the findings.
 
If any of these slit lamp findings are grade 3 or higher, the subject may not continue at this time, but may return up to one additional time to continue. If discontinued a final examination must be completed.
 
If the clearance of the fluorescein needs to be expedited, preservative-free rewetting drops or saline may be instilled.
	
2.4.	Continuance	
Confirm that the entrance slit lamp findings are grade 2 or less.
	
2.5.	Randomization	
Refer to pre-determined randomization order of testing (counter balancing) for the three test treatments. The final contact lens powers found in Visit 1 will be used.
 
 • Test contact lenses with lens-less spectacle frame • OASYS clear contact lenses with lens-less spectacle frame • OASYS clear contact lenses worn with photochromic spectacles 	

Visit 2: Laboratory measures of vision performance			
Step	Procedure	Details	
2.6.	Lens Insertion	The Investigator or the subject inserts the study lenses. Record the time of lens insertion. Check for lens damage under the slit lamp before proceeding with lens settling. Replace damaged lenses if applicable.	
2.7.	Lens Settling	Allow the study lenses to settle for a minimum of 15 minutes.	
2.8.	Pupillometry	Measure the right eye pupil diameter during distance fixation (3 measures) using NeurOptics Pupillometer. EDC: record pupil diameters in mm (0.1 mm increments)	
2.9.	Distance ETDRS LogMAR Visual Acuity	Perform binocular (OU) distance ETDRS logMAR visual acuity test at a 4-meter distance under the following conditions with the study lenses on. The charts will be rotated during testing to reduce memorization. 1. Bright illumination (~500 lux) A. High contrast (90%) chart B. Low contrast (10%) chart 2. Dim illumination (~1 lux) A. High contrast (90%) chart	
2.10.	Contrast Sensitivity Bright Illumination	Perform binocular (OU) contrast sensitivity test under the following conditions with the study lenses on. The Pelli Robson charts will be rotated to reduce memorization. 1. Bright illumination (~500 lux) A. Pelli-Robson chart at 3 meters EDC: record log contrast sensitivity	

Visit 2: Laboratory measures of vision performance			
Step	Procedure	Details	
2.11.	Contrast Sensitivity Dim Illumination	
Perform binocular (OU) contrast sensitivity test under the following conditions with the study lenses on. The Pelli Robson charts will be rotated to reduce memorization.
 
 1. Dim illumination (< ~1 lux) 
 A. Mesotest II instrument B. With glare and without glare C. 4 contrast levels + 5 Landolt C targets per contrast level 
EDC: record the total targets correctly identified with glare and without glare
	
2.12.	Lens Removal	The study lenses will be removed and discarded. A fresh pair of lenses will be used for each trial.	
2.13.	Vison and lens assessments	Repeat 2.5 to 2.12 for the other two treatment conditions	
2.14.	Exit Slit Lamp Biomicroscopy	
FDA Slit Lamp Classification Scale will be used to grade the findings.
 
If any of these slit lamp findings are grade 3 or higher, the subject is classified as having an adverse event. Adverse events shall be documented and followed until resolved, at which time they will be terminated from the study.
 
If the clearance of the fluorescein needs to be expedited, preservative-free rewetting drops or saline may be instilled.
	
2.15.	Exit Visual Acuity	
Record the distance logMAR visual acuity (OD, OS, and OU) to the nearest letter with their habitual correction in place. Subjects must read the smallest line until at least 50% of the letters are read incorrectly.
 
EDC: record logMAR acuity
	

VISIT 3

Visit 3: Closed-circuit on-road driving performance 1 (Day/night condition based on randomization)			
Step	Procedure	Details	
3.1.	Adverse Events and Concomitant Medications Review	Review the subject's concomitant medications and record any changes from the previous study visit. Record any adverse events or medical history changes from the previous study visit.	
3.2.	Practice Driving Lap	Perform familiarization driving lap in habitual spectacle correction in opposite direction to test laps	
3.3.	Entrance Visual Acuity	Record subjects' distance logMAR visual acuity, OD, OS and OU to the nearest letter with habitual correction in place. Subjects must read the smallest line until at least 50% of the letters are read incorrectly. EDC: record logMAR acuity	
3.4.	Entrance Slit Lamp Findings	FDA Slit Lamp Classification Scale will be used to grade the findings. If any of these slit lamp findings are grade 3 or higher, the subject may not continue at this time, but may return up to one additional time to continue. If discontinued a final examination must be completed. If the clearance of the fluorescein needs to be expedited, preservative-free rewetting drops or saline may be instilled.	
3.5.	Continuance	Confirm that the entrance slit lamp findings are grade 2 or less.	

Visit 3: Closed-circuit on-road driving performance 1 (Day/night condition based on randomization)			
Step	Procedure	Details	
3.6.	Randomization	
Refer to pre-determined randomization order of testing (counter balancing) for the three test treatments. The final contact lens powers found in Visit 1 will be used.
 
 • Test contact lenses (worn with spectacle frame without lenses) • OASYS clear contact lenses (worn with spectacle frame without lenses) • OASYS clear contact lenses (worn with photochromic spectacles) 	
3.7.	Lens Insertion	
The Investigator or the subject inserts the study lenses. Record the time of lens insertion. Check for lens damage under the slit lamp before proceeding with lens settling. Replace damaged lenses if applicable.
	
3.8.	Lens Settling	
Allow the study lenses to settle for a minimum of 15 minutes.
 
Note: for nighttime testing, sufficient time is allowed for the subject to dark adapt.
	
3.9.	Pupillometry	
Measure the right eye pupil diameter during distance fixation (3 measures) using NeurOptics Pupillometer while subject seated in vehicle.
 
EDC: record pupil diameters in mm (0.1 mm increments)
	
3.10.	Illuminance levels	
Measurement of lighting level on the track outside the vehicle and at the plane of the eye in the vehicle.
 
 • For daytime testing, the illuminance must be > 1000 lux. • For nighttime testing, the illuminance must be < 10 lux. 
EDC: record outside and inside illuminance in lux rounded to the nearest whole number.
	

Visit 3: Closed-circuit on-road driving performance 1 (Day/night condition based on randomization)			
Step	Procedure	Details	
3.11.	Driving assessment	
Subject performs three laps of the circuit while under assessment. Measurements recorded include:
 
 1. Sign recognition 
 a. EDC: record % signs correctly identified b. EDC: record distance to signs in meters 2. Hazard avoidance 
 a. EDC: record % hazards hit 3. Driving time 
 a. EDC: record lap time in seconds b. EDC: record the % time in wrong lane 4. Pedestrian recognition distance 
 a. EDC: record distance to recognition in meters 
A composite driving Z score will be calculated afterwards using measures listed above.
	
3.12.	Subjective Questionnaire	Administer subjective questionnaire regarding driving task just completed. This will be a paper-administered questionnaire.	Appendix A
3.13.	Lens Removal	The study lenses will be removed and discarded. A fresh pair of lenses will be used for each trial.	
3.14.	Test Treatments 2 and 3	Repeat steps 3.6 to 3.13 for the other testing treatments until all three have been completed.	

Visit 3: Closed-circuit on-road driving performance 1 (Day/night condition based on randomization)			
Step	Procedure	Details	
3.15.	Exit Slit Lamp Findings	
FDA Slit Lamp Classification Scale will be used to grade the findings.
 
If any of these slit lamp findings are grade 3 or higher, the subject is classified as having an adverse event. Adverse events shall be documented and followed until resolved, at which time they will be terminated from the study.
 
If the clearance of the fluorescein needs to be expedited, preservative-free rewetting drops or saline may be instilled.
	
3.16.	Exit Visual Acuity	
Record the distance logMAR visual acuity (OD, OS, and OU) to the nearest letter with their habitual correction in place. Subjects must read the smallest line until at least 50% of the letters are read incorrectly.
 
EDC: record logMAR acuity
	

VISIT 4

Visit 4: Closed-circuit on-road driving performance 2 (Day/night condition based on randomization)			
Step	Procedure	Details	
4.1.	As per Visit 3	Visit 4 follows the same procedures outlined in Visit 3, but is conducted under the opposite condition to Visit 3 (day/night).	

FINAL EVALUATION

The final evaluation will ordinarily take place immediately following the last scheduled follow-up visit per the study protocol. It may also take place at any point the subject discontinues the study or is terminated from the study.

Final Evaluation			
Step	Procedure	Details	
F.1	Final Exam Form	Indicate if the subject completed the study successfully. If subject discontinued from the study indicate the reason.	
F.2	Exit Visual Acuity	Record the distance logMAR visual acuity (OD, OS, and OU) to the nearest letter with their habitual correction in place. Subjects must read the smallest line until at least 50% of the letters are read incorrectly. EDC: record logMAR acuity	

